3. SUBJECT SELECTION

3.1. Inclusion Criteria

- 3.1.1. Subjects must have histologically confirmed diagnosis of multiple myeloma.
- 3.1.2. Subjects must have measurable disease, as defined by at least one of the following:
 - a) Serum monoclonal protein M-protein level ≥ 0.5 g/dL
 - b) Urinary M-protein excretion of ≥ 200 mg over a 24-hour period
 - c) Involved free light chain level ≥ 10 mg/dL, along with an abnormal free light chain ratio
- 3.1.3. Subjects must have disease that has relapsed and/or refractory after their most recent therapy, with progressive disease (PD) being defined as an increase of 25% from the lowest response value in any one or more of the following:
 - a) Serum M-component protein (the absolute increase must be ≥ 0.5 g/dL) and/or
 - b) Urine M-component protein (the absolute increase must be ≥ 200 mg/24 hours) and/or
 - c) Only in subjects without a measurable serum and urine M protein level: the difference between involved and uninvolved free light chain (FLC) levels (absolute increase) must be > 10 mg/dL
 - d) Definite development of new bone lesions or soft tissue plasmacytomas or definite increase in the size of existing bone lesions or soft tissue

plasmacytomas

- e) Development of hypercalcemia (corrected serum calcium >11.5 mg/dL) that can be attributed solely to the plasma cell proliferative disorder.

3.1.4. Subjects with one to three lines of therapy for their disease with a line of therapy defined as one or more cycles of a planned treatment program. Using this definition, treatment with induction therapy, followed by high dose chemotherapy and autologous stem cell transplantation, and finally by maintenance therapy, would constitute one line, provided that multiple myeloma did not meet criteria for progression at any time during this period.

3.1.5. Subjects must have completed their most recent drug therapy directed at multiple myeloma in the following timeframes:

- a) Antitumor therapy (chemotherapy, antibody therapy, molecular targeted therapy, retinoid therapy, hormonal therapy, or investigational agent) at least 21 days prior to C1D1 KRT-232 (AMG 232) + KRd.
- b) Corticosteroids at least 3 weeks prior to starting KRT-232 (AMG 232) + KRd, except for a dose equivalent to dexamethasone of ≤ 4 mg/day
- c) Autologous stem cell transplantation at least 12 weeks prior to starting KRT-232 (AMG 232) + KRd

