10. STUDY CALENDAR

10.1. Part A: Dose Escalation

Cycle (a)	Pre-Cycle	Cycle 1			Cycle 2	Cycle 3-12	Cycle 13-18	Cycle 18+	Post-Cycle
Visit Number	1	2	3	4	5	TBD	TBD	TBD	TBD
Visit Description	Screening	Exam and 1 st dose	Exam	Exam	Exam	Exam	Exam	Exam	EOT (b)
Cycle Day(s)	-28 to 0	1	8	15	1	1	1	1	ND
Visit Window (days)			+/-2	+/-2	+/-4	+/-4	+/-4	+/-4	+/-5
KRT-232 (AMG 232)		A			A	A	A	A	
Carfilzomib		B1			B1	B1	B2		
Lenalidomide		C			C	C	C	C	
Dexamethasone		D			D	D	D	D	
Informed Consent	X								
Demographics	X								
Medical History (c)	X								
Adverse events	X	X	X	X	X	X	X	X	X
Prior/concomitant medications	X	X	X	X	X	X	X	X	X
ECOG performance status	X	X	X	X	X	X	X	X	X
Vital signs	X	X	X	X	X	X	X	X	X
Height	X	X							
Physical Exam, including weight (c)	X	X	X	X	X	X	X	X	X
CBC with diff, platelets	X	X (d)	X	X	X (e)	X (e)	X (e)	X	X
Serum chemistries (f)	X	X (d)	X	X	X (g)	X (g)	X (g)	X	X
aPTT, PT, and INR	X								
Hepatitis panel (h)	X								
Urine or serum β-HCG (i)	X	X	X	X	X	X	X	X	X
Myeloma laboratory assessment (j)	X	X			X	X	X	X	X
Bone marrow aspiration and biopsy (k)	X				X (l)				X (l)
TP53 status (NGS)	X								
Blood sample for drug exposure measurement (m)		X				a			
MIC-1 serum sample (n)	X	X							
Buccal mucosal swab	X								
Blood sample for banking (o)	X								
Myeloma bony survey (p)	X								
Echocardiogram	X								
Dispense KRT-232 (AMG 232)		X			X	X	X	X	X
Pill diaries dispensed/reviewed		X	X	X	X	X	X	X	X

A: KRT-232 (AMG 232), dose as assigned, Day 1 through D7

B1: Carfilzomib 20 mg/m² IV on Days 1 and 2 of Cycle 1, escalating to 27 mg/m² IV on Days 8, 9, 15, 16 of Cycle 1 and continuing on Days 1, 2, 8, 9, 15, 16 of Cycles 2 through Cycle 12

B2: Carfilzomib 27 mg/m² IV on Days 1, 2, 15, and 16

C: Lenalidomide 25 mg PO on Days 1-21

D: Dexamethasone 40 mg PO or IV on Days 1, 8, 15, and 22

- a. Each cycle will last 28 days. Cohort safety assessment for DLTs will be performed after Day 28 of Cycle 1.
- b. End-of-Treatment Visit will occur 30 (\pm 5) days after the last administration of KRT-232 (AMG 232). If the subject begins another form of anticancer therapy before the end of the 30 (\pm 5)-day period, every effort will be made to complete all the End-of-Treatment assessments prior to commencing the new therapy. If there is an abnormality in need of monitoring beyond the End-of-Treatment Visit, subjects will be followed until resolution or confirmed stability of the abnormality.

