- l. Optional bone marrow biopsy and aspiration for Cycle 2/Day 1 may be performed anytime from Cycle 1/Day 24 to Cycle 2/Day 5. Mandatory bone marrow biopsy and aspiration at EOT would be performed within 30 days following the last study treatment, preferably prior to initiating new therapy. In patients achieving a biochemical CR (negative SPEP/UPEP and urine/serum IFE), an additional bone marrow should be performed to confirm a CR with MRD testing using the clonoSEQ® NGS assay (Adaptive Biotechnologies) with minimum sensitivity to 10^{-5} nucleated cells. In patients achieving MRD negativity, a bone marrow biopsy and aspirate may subsequently be performed every 12 months (+/- 30 days) to evaluate for sustained MRD.
- m. Blood samples for drug exposure measurement will be collected Cycle 1/Day 1 pre-dose and post-dose at 1 hr, 3 hr, 5 hr, 8 hr, and 24 hr (C1D2).

- n. Blood samples for MIC-1 testing will be collected at screening, Cycle 1/Day 1 pre-dose, and post-dose at 24 hr (C1D2)
- o. Blood samples for optional biobanking will be collected at screening. Approximately 10 mL of blood will be collected in a heparin (green top) tube and approximately 7 mL of blood will be collected in a red top tube.
- p. One additional bony survey may be performed solely to confirm a CR, if this is indicated by serum and urine immunofixation assays.

ECOG = Eastern Cooperative Oncology Group; EOT = End of Treatment; MIC-1 = macrophage inhibitory cytokine-1; TBD = to be determined.

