15.7. APPENDIX F: IMWG Response Criteria (Kumar et al., 2016)

IMWG MRD criteria (requires a complete response as defined below)	
Sustained MRD-negative	MRD negativity in the marrow (NGF or NGS, or both) and by imaging as defined below, confirmed minimum of 1 year apart. Subsequent evaluations can be used to further specify the duration of negativity (eg, MRD-negative at 5 years)
Flow MRD-negative	Absence of phenotypically aberrant clonal plasma cells by next generation flow (NGF) on bone marrow aspirates using the EuroFlow standard operation procedure for MRD detection in multiple myeloma (or validated equivalent method) with a minimum sensitivity of 1 in 10^5 nucleated cells or higher
Sequencing MRD-negative	Absence of clonal plasma cells by next generation sequencing (NGS) on bone marrow aspirate in which presence of a clone is defined as less than two identical sequencing reads obtained after DNA sequencing of bone marrow aspirates using the LymphoSIGHT platform (or validated equivalent method) with a minimum sensitivity of 1 in 10^5 nucleated cells or higher
Imaging plus MRD-negative	MRD negativity as defined by NGF or NGS plus disappearance of every area of increased tracer uptake found at baseline or a preceding PET/CT or decrease to less mediastinal blood pool SUV or decrease to less than that of surrounding normal tissue
Standard IMWG response criteria	
Stringent complete response	Complete response as defined below plus normal FLC ratio and absence of clonal cells in bone marrow biopsy by immunohistochemistry (κ/λ ratio $\leq 4:1$ or $\geq 1:2$ for κ and λ patients, respectively, after counting ≥ 100 plasma cells)
Complete response	Negative immunofixation on the serum and urine and disappearance of any soft tissue plasmacytomas and $< 5\%$ plasma cells in bone marrow aspirates
Very good partial response	Serum and urine M-protein detectable by immunofixation but not on electrophoresis or $\geq 90\%$ reduction in serum M-protein plus urine M-protein level < 100 mg per 24 h $\geq 50\%$ reduction of serum M-protein plus reduction in 24 h urinary M-protein by $\geq 90\%$ or to < 200 mg per 24 h; If the serum and urine M-protein are unmeasurable, a $\geq 50\%$ decrease in the difference between involved and uninvolved FLC levels is required in place of the M-protein criteria;

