Partial response	If serum and urine M-protein are unmeasurable, and serum-free light assay is also unmeasurable, $\geq 50\%$ reduction in plasma cells is required in place of M-protein, provided baseline bone marrow plasma-cell percentage was $\geq 30\%$. In addition to these criteria, if present at baseline, a $\geq 50\%$ reduction in the size (SPD) of soft tissue plasmacytomas is also required
Minimal response	$\geq 25\%$ but $\leq 49\%$ reduction of serum M-protein and reduction in 24-h urine M-protein by 50–89%. In addition to the above listed criteria, if present at baseline, a $\geq 50\%$ reduction in the size (SPD) of soft tissue plasmacytomas is also required
Stable disease	Not meeting criteria for complete response, very good partial response, partial response, minimal response, or progressive disease Any one or more of the following criteria: Increase of 25% from lowest confirmed response value in one or more of the following criteria: Serum M-protein (absolute increase must be ≥ 0.5 g/dL); Serum M-protein increase ≥ 1 g/dL, if the lowest M component was ≥ 5 g/dL; Urine M-protein (absolute increase must be ≥ 200 mg/24 h);
Progressive disease	In patients without measurable serum and urine M-protein levels, the difference between involved and uninvolved FLC levels (absolute increase must be > 10 mg/dL); In patients without measurable serum and urine M-protein levels and without measurable involved FLC levels, bone marrow plasma-cell percentage irrespective of baseline status (absolute increase must be $\geq 10\%$); Appearance of a new lesion(s), $\geq 50\%$ increase from nadir in SPD of > 1 lesion, or $\geq 50\%$

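### Appendix F ties response and progression to plasmacytomas and lesions, but the calendars plan only a screening bony survey and one optional repeat limited to confirming CR

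*Combined protocol and SAP*

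**What the plan says.** **Criteria.** Section 11.1 makes the IMWG criteria in Appendix F (15.7) the standard, with re-evaluation every 4 weeks. In Appendix F:
- CR calls for "Negative immunofixation on the serum and urine and disappearance of any soft tissue plasmacytomas", together with a marrow condition.
- PR and MR add to their laboratory criteria that, where plasmacytomas were present at baseline, at least a 50% "reduction in the size (SPD) of soft tissue plasmacytomas is also required".
- Progression is met by any one of several routes. These include a new lesion or measured growth of a known one.

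**Entry.** Section 3.1.3(d) accepts, as one of five ways to show progression on the last therapy, "Definite development of new bone lesions or soft tissue plasmacytomas" or definite growth of existing ones. Among disease sites, only known central nervous system involvement is excluded (3.2.6).

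**Imaging.** The calendars in 10.1 and 10.2 mark a myeloma bony survey at screening and at no later visit. Neither has a row for CT, MRI or PET/CT. Footnote p, identical in both parts, states: "One additional bony survey may be performed solely to confirm a CR, if this is indicated by serum and urine immunofixation assays". Footnote c makes physical examinations after screening symptom-directed. Section 11.2, for other response parameters, is marked not applicable.

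**Analysis.** Section 13.6 defines overall response as PR or better across all cycles. It takes investigator-determined IMWG progression or death as the PFS event, and censors subjects without an event at their last myeloma disease assessment. It gives no rule for missing lesion data.

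**The concern.** The plan adopts criteria that need a lesion measurement at baseline and again on treatment, admits subjects to whom those criteria apply, and then plans no on-treatment measurement except an optional one tied to CR. A site that follows the calendar exactly has laboratory results every cycle but nothing planned with which to check the plasmacytoma clause for PR or MR, or to find a new or growing lesion while M-protein and light chains stay controlled.

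Overall response rate is the first secondary objective of Part B (1.2.2), and 13.3 states its precision. If a persisting plasmacytoma goes unmeasured, a laboratory response may be recorded as an IMWG response. If a lesion-only progression goes unseen, response duration and PFS run on until a laboratory marker rises, the subject dies, or follow-up is censored. Both errors favour the treatment.

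**Working it through.** **1. The plan's own precision figure (13.3).** It gives a maximum half-width of the 95% interval for the response rate of 32% for 10 subjects and 25% for 16. At a rate of 0.5 the half-width is z × √(0.25/n).
- With z = 2: 2 × √(0.25/10) = 31.6% and 2 × √(0.25/16) = 25.0%.
- With z = 1.96: 31.0% and 24.5%.
- Exact (Clopper-Pearson) maximum: 31.3% and 25.3%.

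The stated figures reproduce. They describe sampling error only and contain nothing for misclassification.

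**2. Criteria set against planned assessments.**

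| Category | Lesion condition in Appendix F | Planned measurement |
|---|---|---|
| CR | plasmacytomas gone | one optional survey, modality undefined |
| VGPR | none as printed | not needed as printed |
| PR, MR | at least 50% SPD reduction if present at baseline | none on treatment |
| Progression, laboratory routes | none | M-protein and light chains on Day 1 of each cycle and at end of treatment |
| Progression, lesion route | new lesion or measured growth | none |

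The gap lies in PR and MR for subjects with a baseline plasmacytoma, and in the lesion route to progression. CR is partly covered. MR affects the best-response table but not the overall response rate, which starts at PR.

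**3. An overlap inside Appendix F.** New plasmacytomas or bone lesions also appear under clinical relapse, which the appendix says is not used for PFS. A new lesion under progressive disease does count. The plan does not say which entry governs when a lesion is found.

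**4. Size.** One misclassified subject moves the response rate by 1/10 = 10 points, or by 1/16 = 6.25 points when the six escalation subjects at the MTD are included. The documents give no share of subjects with a plasmacytoma at entry, so the shares q below are assumptions. Expected number affected is n × q, and the chance of at least one is 1 − (1 − q)^n.

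| Assumed q | Expected, n = 10 | At least one, n = 10 | Expected, n = 16 | At least one, n = 16 |
|---|---|---|---|---|
| 5% | 0.5 | 40% | 0.8 | 56% |
| 10% | 1 | 65% | 1.6 | 81% |
| 20% | 2 | 89% | 3.2 | 97% |

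These are chances of having such a subject, not of misclassifying one.

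**The case against.** The strongest reply is that unscheduled does not mean unassessed. Section 11.1 requires investigators to apply Appendix F, so recording PR with a known, unmeasured plasmacytoma would breach the criteria. Footnote p restricts the additional bony survey and does not forbid clinically indicated CT, MRI or PET/CT. A palpable mass may be found on examination. This stands, and it is why the finding concerns the absence of a planned assessment, not the impossibility of one. It does not close the gap: whether the clause is checked is left to local practice, the only imaging text points the other way, and 13.6 has no rule for missing lesion data.

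Four stronger readings are tempting, and the documents do not support them.
- A reader might infer that PFS cannot be determined. Section 3.1.2 requires every subject to have measurable serum M-protein, urine M-protein or free light chains. These are measured each cycle, any one route suffices for progression, and death is an event.
- A reader might infer that all reported responses are merely biochemical. Without a plasmacytoma, the Appendix F criteria for PR rest mainly on M-protein and light chains anyway, and a biochemical CR triggers a confirmatory marrow.
- A reader might extend the gap to VGPR. The printed definition has no plasmacytoma clause.
- A reader might say that the survey cannot show soft tissue. The documents leave its modality undefined, so they do not settle this.

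It is also fair to say that no go/no-go threshold rests on the response rate and that planned precision is already wide. That limits the severity. It does not excuse a one-directional error that the interval does not reflect.

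**Conclusion.** The mismatch is real but confined to a subgroup. For subjects with a plasmacytoma at baseline, no planned measurement supports PR or MR. For any subject, progression seen only in a lesion has no planned detection. Overall response rate, duration of response and PFS may therefore be biased upward, by 10 or 6.25 response-rate points for each subject misclassified among 10 or 16. The total effect cannot be sized from the documents, because it depends on an unstated prevalence and on how often sites image outside the calendar. The primary safety and MTD objectives are untouched. This should be corrected, but it does not threaten the trial's main purpose.

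**What to change.** 1. **Footnote p in 10.1 and 10.2:** remove the limit to CR confirmation and reconcile the footnote with Appendix F, so that standard-of-care repeat imaging in subjects with baseline plasmacytomas or lesions can be used for PR, MR and progression. State the survey modality. No new mandatory imaging is needed.
2. **Screening record:** capture the presence and size of any plasmacytoma for every subject, whatever the route of entry. Relying on 3.1.3(d) paperwork would miss subjects who qualify by routes (a), (b), (c) or (e).
3. **Section 13.6, progression:** state that a lesion meeting the Appendix F progression thresholds on any imaging counts as progression on the imaging date, and resolve the overlap with clinical relapse.
4. **Section 13.6, response:** report responses in subjects whose baseline plasmacytoma was not re-measured separately, labelled as biochemical response with IMWG status not verified. Say whether VGPR falls under this, since its printed definition is silent. Add a sensitivity response rate that counts these subjects as non-responders.

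The non-responder count should not be the only rule, because it would replace possible upward bias with downward bias. Section 2.4.3 cites an 87.1% response rate for KRd alone, so many affected subjects could be true responders. At the assumed 5–20% share, the expected count of 0.5–2 of 10, at 10 points each, could lower the rate by up to 5–20 points.

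The cost is one CRF field, a footnote edit, some wording in 13.6, one extra sensitivity analysis, and a possibly lower verified response rate.

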10.2. Part B: Dose Expansion

Cycle (a)	Pre-Cycle	Cycle 1			Cycle 2	Cycle 3-12	Cycle 13-18	Cycle 18+	Post-Cycle
Visit Number	1	2	3	4	5	TBD	TBD	TBD	TBD
Visit Description	Screening	Exam and 1 st dose	Exam	Exam	Exam	Exam	Exam	Exam	EOT (b)
Cycle Day(s)	-28 to 0	1	8	15	1	1	1	1	ND
Visit Window (days)			+/-2	+/-2	+/-4	+/-4	+/-4	+/-4	+/-5
KRT-232 (AMG 232)		A			A	A	A	A	
Carfilzomib		B1			B1	B1	B2		
Lenalidomide		C			C	C	C	C	
Dexamethasone		D			D	D	D	D	
Informed Consent	X								
Demographics	X								
Medical History (c)	X								
Adverse events	X	X	X	X	X	X	X	X	X
Prior/concomitant medications	X	X	X	X	X	X	X	X	X
ECOG performance status	X	X	X	X	X	X	X	X	X
Vital signs	X	X	X	X	X	X	X	X	X
Height	X	X							
Physical Exam, including weight (c)	X	X	X	X	X	X	X	X	X
CBC with diff, platelets	X	X (d)	X	X	X (e)	X (e)	X (e)	X	X
Serum chemistries (f)	X	X (d)	X	X	X (g)	X (g)	X (g)	X	X
aPTT, PT, and INR	X								
Hepatitis panel (h)	X								
Urine or serum β-HCG (i)	X	X	X	X	X	X	X	X	X
Myeloma laboratory assessment (j)	X	X			X	X	X	X	X
Bone marrow aspiration and biopsy (k)	X				X (l)				X (l)
TP53 status (NGS)	X								
Blood sample for drug exposure measurement (m)		X				a			
MIC-1 serum sample (n)	X	X							
Buccal mucosal swab	X								
Blood sample for banking (o)	X								
Myeloma bony survey (p)	X								
Echocardiogram	X								
Dispense KRT-232 (AMG 232)		X			X	X	X	X	X
Pill diaries dispensed/reviewed		X	X	X	X	X	X	X	X

A: KRT-232 (AMG 232), dose as assigned, Day 1 through D7

B1: Carfilzomib 20 mg/m² IV on Days 1 and 2 of Cycle 1, escalating to 27 mg/m² IV on Days 8, 9, 15, 16 of Cycle 1 and continuing on Days 1, 2, 8, 9, 15, 16 of Cycles 2 through

Cycle 12

B2: Carfilzomib 27 mg/m² IV on Days 1, 2, 15, and 16

C: Lenalidomide 25 mg PO on Days 1-21

D: Dexamethasone 40 mg PO or IV on Days 1, 8, 15, and 22

- a. Each cycle will last 28 days. Cohort safety assessment for DLTs will be performed after Day 28 of Cycle 1.
- b. End-of-Treatment Visit will occur 30 (\pm 5) days after the last administration of KRT-232 (AMG 232). If the subject begins another form of anticancer therapy before the end of the 30 (\pm 5)-day period, every effort will be made to complete all the End-of-Treatment assessments prior to commencing the new therapy. If there is an abnormality in need of monitoring beyond the End-of-Treatment Visit, subjects will be followed until resolution or confirmed stability of the abnormality.
- c. A complete history & physical examination should be performed at screening. Thereafter, only a symptom-directed physical exam is required.
- d. CBC and serum chemistries for Cycle 1/Day 1 pre-dose can be collected within 48 hours before the first dose.
- e. CBC are collected pretreatment (within 48 hours) on Days 8 and 15 during Cycles 2-12 and Day 15 during Cycles 13-18.
- f. Serum chemistries: Albumin, alkaline phosphatase, total bilirubin, bicarbonate, BUN, calcium, chloride, creatinine, glucose, LDH, phosphorus, potassium, total protein, SGOT [AST], SGPT [ALT], sodium, magnesium.
- g. Basic Metabolic Panel (bicarbonate, BUN, calcium, chloride, creatinine, glucose, potassium, sodium) are collected pretreatment (within 48 hours) on Days 8 and 15 during Cycles 2-12 and Day 15 during Cycles 13-18.
- h. Hepatitis panel will include HAV Ab, qualitative HBsAb, HBsAg, HBcAb, and HCV Ab
- i. Two negative pregnancy tests must be obtained prior to initiating therapy in female subjects of childbearing potential during the screening period. The first test should be performed within 10-14 days and the second test within 24 hours prior to initiating therapy and then weekly during the first month, then monthly thereafter in women with regular menstrual cycles or every 2 weeks in women with irregular menstrual cycles as per the lenalidomide Risk Evaluation and Mitigation Strategy (REMS) program.
- j. Myeloma laboratory assessment includes serum free light-chain assay, serum protein electrophoresis (and immunofixation if needed to confirm CR if no M-protein detected on electrophoresis), serum quantitative immunoglobulins (IgG, IgA, IgM), 24-hour urine protein electrophoresis (and immunofixation if needed to confirm CR if no M-protein detected on electrophoresis), and β 2-microglobulin. Initial pretreatment assessment can be collected within 1 week of first dose.
- k. Initial pretreatment/screening bone assessment requires bilateral biopsy and aspirates. Can occur within 4 weeks of first dose date. Bone marrow analysis should include morphologic review, quantification of percentage of plasma cells, flow cytometry, and myeloma fluorescence *in situ* hybridization (FISH) panel (performed locally) as per standard of care.
- l. Optional bone marrow biopsy and aspiration for Cycle 2/Day 1 may be performed anytime from Cycle 1/Day 24 to Cycle 2/Day 5. Mandatory bone marrow biopsy and aspiration at EOT would be performed within 30 days following the last study treatment, preferably prior to initiating new therapy. In patients achieving a biochemical CR (negative SPEP/UPEP and urine/serum IFE), an additional bone marrow should be performed to confirm a CR with MRD testing using the clonoSEQ® NGS assay (Adaptive Biotechnologies) with minimum sensitivity to 10^{-5} nucleated cells. In patients achieving MRD negativity, a bone marrow biopsy and aspirate may subsequently be performed every 12 months (+/- 30 days) to evaluate for sustained MRD.
- m. Blood samples for drug exposure measurement will be collected Cycle 1/Day 1 pre-dose and post-dose at 1 hr, 3 hr, 5 hr, 8 hr, and 24 hr (C1D2).
- n. Blood samples for MIC-1 testing will be collected at screening, Cycle 1/Day 1 pre-dose, and post-dose at 24 hr (C1D2)

- o. Blood samples for optional biobanking will be collected at screening. Approximately 10 mL of blood will be collected in a heparin (green top) tube and approximately 7 mL of blood will be collected in a red top tube.
- p. One additional bony survey may be performed solely to confirm a CR, if this is indicated by serum and urine immunofixation assays.

ECOG = Eastern Cooperative Oncology Group; EOT = End of Treatment; MIC-1 = macrophage inhibitory cytokine-1; TBD = to be determined.

